Evaluating the statistical power for a mixed model longitudinal analysis is not straightforward. One conservative approach is to power the study with regard to a simple effects test associated with the highest order effect of interest in the study, here the Treatment x Assessment Time interaction. In this case, the sample size for the two treatment groups is estimated and, since the two treatment groups are not matched, the sample size per treatment group is likely to be larger than would be required to establish a significant change in outcome within a Treatment group across Assessment Time simple effects test (e.g., difference in SRS scores from baseline to 2-year follow-up). Accordingly, this study was powered with respect to the simple effects tests associated with a significant Treatment x Assessment Time interaction at the primary 2-year endpoint. This power analysis is informed by the data already gathered by the SDRG with the mean and standard error estimated adjusted for SRS baseline and patient age gender and Cobb angle. **Table 2 summarizes estimated sample sizes per treatment needed to achieve power of .80 for 2-tailed testing with type I error rate set at .05 under a variety of effect sizes, based on mean and standard deviation estimates.** The two rows highlighted were judged to reflect the most likely scenarios and, overall, the sample size of 30 per group in the RCT was considered a reasonable choice for achieving sufficient power to detect a real difference between the two treatment groups at 2-years follow-up.

Table 2

Estimated Means		Common SD	Effect Size	N per Group
Trt 1	Trt 2			
0.3	0.8	0.6	0.833	24
0.4	0.8	0.6	0.667	37
0.5	0.8	0.6	0.500	64
0.3	0.8	0.7	0.714	32
0.4	0.8	0.7	0.571	50
0.5	0.8	0.7	0.429	87

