1.6.3 Participants Available for Recruitment and Power. From the beginning of 2004 through the end of 2006, the five participating sites enrolled 155 non-operative patients and 141 operative patients meeting the criteria for diagnoses, symptoms and age required for this study (Table 3, next page). These preliminary data show a consistent recruitment level that should allow us to enroll our estimated 300 total subjects. The SDG group estimates that over 90% of patients are willing to participate in a clinical trial, with 30% of those willing to randomize. If, over the course of 3 years, 300 patients are eligible, then an estimated 270 (90% of 300) would be willing to participate, with 82 of these (30% of 270) willing to randomize. With 1:1 randomization to operative and non-operative treatments, at the end of 3 years, 41 patients would be randomized into each of the operative and non-operative arms. With 20% crossover in the non-operative arm, there would be three treatment groups: 41 in operative, 33 in non-operative, and 8 cross-overs from operative to non-operative, although in an intent-to-treat analysis all of these crossovers would be retained in their initially assigned group. Assuming a 10% loss to follow-up by 2-years, these numbers are reduced to 36, 30, and 7 for the operative, non-operative and crossover groups, respectively. Based on Table 2 (above), as shown in the “boxed” rows, the 80% power to detect effects sizes at or above 0.714 and 0.814 would still apply to the RCT. Further, within the longitudinal analysis structure, patient data remains to inform the model for every follow-up assessment.

gathered, and therefore, a patient's loss to follow-up does not negate the information that they provided up to that point, thus providing additional precision to estimates that will boost statistical power.

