From the study power analysis, power of 80% to detect an effect size between .667 - .714 with type I error rate set at .05 and 2-tailed testing requires a sample size of 32 – 37 patients per treatment group. We plan (are budgeted) to enroll 300 patients overall and expect about 100 (1/3) of these patients to be randomized. For the purposes of a stopping rule, N counts needed to establish power greater than 70 are more reasonable given stopping a study for futility is quite different than stopping rules associated with safety considerations. Power of 70% with an effect size of .667 requires 29 patients per group. A calculator estimating the probability of obtaining at least 58 patients from a sample of 300 enrolled patients under various recruitment and attrition scenarios

Based on this calculator results, futility risk (i.e., the inability to recruit at least 58 patients into the RCT) is quite high if, after 100 recruited patients, RCT recruitment is at no more than 20%, even if attrition rates are as low as 10%. When RCT recruitment rates are up to 25%, futility risks are relatively low when attrition rates are also low ($\leq 15\%$) but otherwise probability of successful recruitment are low. When RCT recruitment rates reach 30% for the first 100 enrollees, the probabilities of successful recruiting at least 58 patients is quite good, as long as attrition rates remain no greater than 30%.

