In sum, if we calculate the recruitment and attrition rates in RCT study after 100 patients have been enrolled we can estimate the likelihood of attaining an RCT sample size of at least 58, which would result in power in the 70% range. If likelihoods of attaining sufficient patients are low based on the first 100 patients enrolled, the choices are: 1) stop the RCT enrollment; or 2) close the preference trial when 200 patient shave been enrolled and continue to recruit into the RCT. The decision to continue enrolling the RCT after the preference trial has closed is predicated on assumptions that a) patients might be more willing to enroll into the RCT given there is no other study choice; and b) the nature of the patients enrolling into the RCT after the preference trial has closed are from the same population. Therefore, if the second choice is taken, a subsequent futility stopping rule for the RCT would be in force. This stopping rule will include two arms: 1) the same as the first stopping rule regarding recruitment and attrition and 2) an evaluation of the similarity of the RCT patients enrolling prior to and following the closing of the preference trial.

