Treadmill evaluation. Again, longitudinal mixed model regression analysis will be used to evaluate the treadmill evaluation. However, since crossover to surgery will trigger a “new” baseline treadmill test, these patients will be repeated in the analysis with their 2nd baseline considered their follow-up treadmill test relative to the 1st baseline score and their final treadmill test 2 years following their 2nd baseline treadmill test will be considered their follow-up treadmill test relative to their 2nd baseline treadmill test.

Treadmill = treatment | interval| time site age sex

Treadmill = treatment | T_DOI(interval) site age sex

Patients who crossed over to surgery will be provided with a second DOI value (DOI_cNS) that will be used in conjunction with the date of the follow-up treadmill test to define the delta associated with the 2 year interval data form used to gather the follow-up treadmill score.

Addendum 1/17/13: Sample Size Calculation.

A sample size of 82 patients (41 per treatment arm) was estimated to provide 80% power with an SRS-22 effect size of ≥ 0.714 , 10% loss-to-follow-up at 2 years postoperative, and 20% crossover from nonoperative to operative intervention, based upon a mixed-model longitudinal analysis accounting for repeated measures at follow-up. A priori sample size estimations require estimates of outcome variances that may be inaccurate in the actual population studied. To account for this a bootstrap sample size estimation using data from the first 26 patients randomized was performed to provide a more accurate assessment of the required sample size needed to address the original trial aims, to include both the SRS-QOL and ODI.

Sample Size Estimation

Interval	ODI Power	SRS Power	n/GRP
3 months	0.0390	0.6770	18
6 months	0.7270	0.9980	
9 months	0.5600	1.0000	
12 months	0.8170	0.9950	

These results suggested that >80% power could be achieved to address Aim #1 with 36 randomized patients (18 patients per group).

Enrollment in the Observational cohort closed May 2013. Enrollment in the randomized cohort closed July 2014 with 63 participants, 70% of the original enrollment goal, this enrollment goal was felt, based on the above sample size analyses, to allow for sufficient power making allowances for loss to follow-up and cross-over over time.

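### The futility threshold of 58 randomised patients carries about 70% power only if nobody crosses over; with the plan's 20% crossover it is about 51–67%, and the randomisation goal is stated inconsistently

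*SAP*

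**What the plan says.** **The threshold.** SAP 1.6.4 accepts 70% power as enough for a futility decision and states: "Power of 70% with an effect size of .667 requires 29 patients per group". The rule then looks, after 100 patients have enrolled, at the chance of "attaining an RCT sample size of at least 58, which would result in power in the 70% range". The calculator behind it varies recruitment and attrition over 300 enrolled patients. Crossover is not mentioned.

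**Crossover.** SAP 1.6.3 assumes 20% crossover in the non-operative arm and says that, under intent-to-treat, crossovers stay where they were assigned. SAP 1.6.1 (Stage 3, Aim 1, primary analyses) makes intent-to-treat primary in the randomised cohort, and the addendum of 8/29/12 repeats it. The addendum of 1/17/13 also gives 20%, from nonoperative to operative.

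**Enrolment base.** SAP 1.6.3 takes 300 eligible patients, 270 of them willing to participate, "with 82 of these (30% of 270) willing to randomize". Protocol 1.0 likewise gives about 82 randomised and 188 observational. SAP 1.6.4 says: "We plan (are budgeted) to enroll 300 patients overall and expect about 100 (1/3) of these patients to be randomized". The addendum of 1/17/13 reports: "Enrollment in the randomized cohort closed July 2014 with 63 participants, 70% of the original enrollment goal".

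**The concern.** Under intent-to-treat, a patient assigned to non-operative care who has surgery and benefits from it raises the non-operative mean and narrows the contrast. SAP 1.6.3 reflects crossover only by splitting the counts into 41, 33 and 8; the effect size stays undiluted. SAP 1.6.4 then takes the undiluted 0.667 and does not mention crossover at all.

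The threshold is meant to mark the smallest randomised comparison worth continuing. If 58 patients carry materially less than 70% power under the plan's own assumptions, the rule could let the comparison continue at a size that the sponsor had meant to regard as too small.

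The enrolment base matters for a related reason. The rule turns a randomisation rate and an attrition rate into a probability of reaching 58, and that probability depends strongly on how many patients are to be enrolled.

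**Working it through.** **Inputs from the documents.** Two-sided alpha 0.05 (1.6.4: "with type I error rate set at .05 and 2-tailed testing requires a sample size of" 32–37 per group). Effect size 0.667 is the Table 2 row "0.4 0.8 0.6 0.667 37"; 0.714 is the row "0.3 0.8 0.7 0.714 32". These are the two ends of the range given in 1.6.4. Allocation is 1:1 and crossover is 20% (1.6.3).

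**Input assumed.** The share *b* of the surgical benefit that crossovers obtain by the analysis time. The documents give none, so *b* = 0.5 and *b* = 1 are shown.

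**Step 1: reproduce the plan.** For a two-sample t-test with *n* per group, the noncentrality is d × √(n/2) on 2n − 2 degrees of freedom. With n = 29, √14.5 = 3.808, df = 56 and the critical value is 2.003. At d = 0.667 the noncentrality is 2.540 and power is 70.4%. Solving for 70% gives 28.7, so 29 per group. All six sample sizes in Table 2 reproduce by the same method.

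**Step 2: add 20% crossover under intent-to-treat.** Diluted effect = d × (1 − 0.20 × b).

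| d | b | Diluted d | Noncentrality | Power at 29 per group |
|---|---|---|---|---|
| 0.667 | no crossover | 0.667 | 2.540 | 70.4% |
| 0.667 | 0.5 | 0.600 | 2.286 | 61.3% |
| 0.667 | 1 | 0.534 | 2.032 | 51.5% |
| 0.714 | no crossover | 0.714 | 2.719 | 76.2% |
| 0.714 | 0.5 | 0.643 | 2.447 | 67.2% |
| 0.714 | 1 | 0.571 | 2.175 | 57.1% |

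Mixing crossovers with non-crossovers also widens the spread in the non-operative arm. For the 0.667 row with full benefit, the non-operative mean is 0.8 × 0.4 + 0.2 × 0.8 = 0.48 and its variance is 0.36 + 0.2 × 0.8 × 0.4² = 0.3856. The pooled SD is √((0.3856 + 0.36)/2) = 0.611, so d = 0.32/0.611 = 0.524 and power is 50.1%. A simulation gave 50.2%. This refinement changes little.

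For scale, 70% power at d = 0.667 would need 36 per group at b = 0.5 (35.2 rounded up) and 45 at b = 1 (44.3 rounded up).

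**Step 3: the enrolment base.** 300 × 1/3 = 100, against 270 × 0.30 = 81 (written as 82). The calculator's output is not shown, so I rebuilt it as P(X ≥ 58) with X ~ Binomial(N, randomisation rate × (1 − attrition)), which reads 58 as the count after attrition.

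| Randomised, attrition | How 1.6.4 describes it | N = 300 | N = 270 |
|---|---|---|---|
| 20%, 10% | high futility risk | 0.30 | 0.08 |
| 25%, 15% | relatively low futility risk | 0.81 | 0.49 |
| 30%, 30% | good prospects | 0.78 | 0.45 |

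The N = 300 column agrees with the SAP's descriptions, which supports the reconstruction.

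**Step 4: the 70% at closure.** 63/82 = 77%; 63/100 = 63%; 63/90 = 70%. Ninety is 30% of 300, but neither document states it as a goal.

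**Step 5: crossover direction.** SAP 1.6.3 places the 20% in the non-operative arm, and its counts agree (41 − 8 = 33 remain non-operative). The same sentence then describes the 8 as moving from operative to non-operative. The addendum of 1/17/13 has the opposite direction.

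**The case against.** **A reader might infer that the 70% was miscalculated.** It was not; it follows exactly from the inputs stated. What is missing is an allowance for crossover.

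**A reader might take 51% as the trial's real power at 58.** The documents do not support one figure. That value needs the lower effect size and full surgical benefit in every crossover, and neither document states that benefit. The documents also do not say whether the Table 2 effects are before or after dilution, and the addendum of 1/17/13 presents its 80% as already allowing for 20% crossover. If the effects were meant as diluted ones, 70% would stand, but nothing in 1.6.2 to 1.6.4 says so.

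**Crossover could be handled by removing patients**, as the counts in 1.6.3 suggest. With 29 against 23, power is 64.9% at 0.667 and 70.8% at 0.714. That does not match an intent-to-treat analysis, which keeps these patients in their assigned arm.

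**Repeated measures and baseline covariates should add power.** The SAP says so but gives no figure, and 1.6.2 says the planning estimates were already adjusted for baseline SRS, age, gender and Cobb angle. No credit can be quantified.

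**A reader might conclude that 270 is the right base and that the calculator wrongly assumed 100 randomised.** Neither follows. An enrolment target of 300 appears in Protocol 1.0, SAP 1.6.3 and SAP 1.6.4, so 300 may be the intended base, and on 300 the SAP's descriptions hold. The figure of about 100 is an expectation; the rule itself uses the rate seen in the first 100 enrolled.

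**A reader might extend the point to the claim of sufficient power at closure.** The addendum of 1/17/13 rests that claim on the 82-patient calculation and the bootstrap estimate, not on the threshold of 58. Both cohorts are also recorded as closed, so a corrected rule can no longer change the decision to continue. This lowers the urgency. It does not make the stated power right.

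**Conclusion.** The point holds as an omitted assumption behind a decision threshold. With the planned 20% crossover and intent-to-treat analysis, 29 per group gives about 61% to 51% power at effect size 0.667 and about 67% to 57% at 0.714, taking half to full surgical benefit in crossovers. All four values are below 70%. They rest on a two-sided t-test at 0.05, on reading Table 2 effects as undiluted, on 58 being evaluable patients, and on an assumed benefit share.

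The inconsistency in the base also holds, in a limited form: 82 and about 100 cannot both be the expected number randomised, 300 is used for both eligible and enrolled patients, and the 70% at closure matches only an unstated goal of 90. If the enrolled base is 270, two scenarios that the SAP treats as favourable fall to slightly less than an even chance. The documents do not settle whether it is.

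**What to change.** 1. In SAP 1.6.4, restate the power at 58 evaluable patients as about 51–67% under the planned 20% crossover, and give the assumed benefit to crossovers beside it. If the Table 2 effects already include dilution, say so and give the basis.
2. Reconcile Protocol 1.0, SAP 1.6.3 and SAP 1.6.4 on whether 300 means eligible or enrolled, and on whether 82, 90 or 100 is the randomisation goal.
3. If the enrolled base proves to be 270, re-run the futility probabilities and revise the descriptions in 1.6.4.
4. Give the denominator for the 70% in the addendum of 1/17/13.
5. Reconcile the crossover direction in SAP 1.6.3 with the rest of its own sentence and with that addendum.

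The cost is SAP wording and, at most, one re-run of the existing calculator. No change to design, data collection or patient care is involved. The stated power at the threshold becomes less favourable, and so do the futility probabilities if the base is 270. With enrolment closed, the gain is an accurate record of what the threshold guaranteed.

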2. the detection of the relevant eligibility violations can be made completely objectively;
3. all subjects receive equal scrutiny for eligibility violations; and
4. all detected violations of the particular entry criterion are excluded.

The study management plan is explicitly designed to minimize these events. Specifically, there will be electronic registration by site coordinator with explicit inclusion and exclusion criteria assessment on the enrollment form and review of registration by the Project Manager (PM) at Washington University.

In the observational cohort, the choice of nonoperative vs. operative care will be made by the patient guided by the provider's recommendation and presentation of existing data regarding nonoperative and operative care based on the following parameters: Patients with clinical symptoms of pain and functional limitations that are well controlled with non-operative care will be encouraged to pursue nonoperative care. Patients who have not demonstrated access or utilization to previous nonoperative care for their symptoms will be directed to non-operative care as an initial treatment. Enrollments into the observational arms will be closed when each arm's sample size is reached in order to achieve equal numbers of patients in each arm at the conclusion of the study.

**1.4 Study Interventions:** Regardless of study cohort participation (randomized or observational), interventions will not be implemented until the PM has confirmed appropriate enrollment. Nonoperative interventions will then be implemented as soon as possible. Due to the length and complexity of spinal deformity procedures, available dates for elective operative procedures may range from 1 to 6 months. Therefore, operative intervention will take place within six months of treatment assignment but baseline assessments, specifically MD assessment, patient reported HRQOL and treadmill tests must be completed within 6 months prior to intervention. Standardized protocol guidelines for nonoperative and operative treatment, as detailed below, will be followed by all sites.

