**1.5.2 Data Collection Procedures:** Site research coordinators will identify, consent and enroll eligible participants in the study. After obtaining patient consent, the site coordinator will electronically register participants through a secure Web site. Registration information will include demographic information and documentation of inclusion criteria to minimize inappropriate enrollment. Randomization software will generate an intervention assignment upon completion of registration for patients agreeing to randomization. Site coordinators will notify the PM of patient enrollment via alpha pager. Site coordinators will provide questionnaire packages at study entry (all patients), at 3 months post-treatment and at each annual post-treatment clinical visit. In addition, questionnaire packets will be mailed to participants at 6, 9, 15, 18, 21, 30, 42 & 72 months post-intervention to enhance patient tracking. A self-addressed, stamped envelope will be provided for return of questionnaires. Therefore, patients will complete HRQOL at baseline and every 3 months post-intervention for the first 2 years, every 6 months years 3 & 4 and annually thereafter.

Radiographic images will also be electronically uploaded to the database for measurement, future retrieval and review. An independent, blinded, experienced orthopedic spine surgeon will perform radiographic measurements at baseline and at annual follow-up visits. The surgeon will be blinded to patient, site and surgeon identification and he will not enroll or treat any study participants, thus eliminating the potential threat for bias if sites measured their own patient films. In addition, the blinded surgeon will assess fusion mass on participants receiving surgical treatment by reviewing radiographic images (standing AP and lateral, right and left oblique views of the surgical site, and, if fused to the sacrum, a Ferguson AP L5-S1). Results will be recorded on the Radiographic Assessment form and entered into the database. In addition, Clinical Assessment forms will be completed at baseline and annual follow-up visits to document physical and medical findings, including adverse events and complications.

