Data capture will occur via REDCap, a secure Web-based data input interface available in each participating center's research facility. This Web-based secure data capture, data storage and data transmission system is maintained by Washington University. To improve data accuracy, double data entry will be implemented. Immediate data clarifications will be generated at the time of data entry for missing responses, out-of-range responses, and/or inconsistencies in responses that break established validity rules. The REDCap application is fully HIPAA-(Health Insurance Portability Accountability Act) compliant and will have thorough testing and validation processes in place. Baseline data will be entered within 24 hours of enrollment, before study interventions are activated. Follow-up data will be entered within 1 week of a patient's visit.

Site coordinators and PIs will receive a monthly Upcoming Events Report via email. This report will be generated by the PM and include any patient who will be due for a clinic visit in the upcoming 3 months. Site coordinators will have the capability to run this report more frequently, if they choose. This will allow site coordinators adequate time to contact and arrange for appropriate scheduling, including functional treadmill testing at the 2-year follow-up. The report will also include all patients who will require HRQOL mailings in the upcoming month. Site coordinators will be responsible for mailing, tracking return of and entering data from the questionnaires. Failure to obtain and store data on patients within a 1-week period of the expected encounter windows will be monitored by the PM through weekly database queries. The PM will follow up with the site coordinator to further investigate these situations. Weekly reports of patients with past due follow-up will be sent to the site coordinator and PI.

Patients will be encouraged to return to the primary center for examination, radiographs and questionnaires at the designated intervals. If the patient is unable to return to the center, they will be

encouraged to complete questionnaires and radiographic studies locally and mail them to the primary center at the intervals required by the study protocol.

Acceptable windows for data collection are as follows:

**Baseline** data must be completed prior to intervention initiation, specifically:

- Site and patient completed forms, functional treadmill test completed within 6 months prior intervention initiation,

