Addendum 8/29/12: (modified and edited 6/19/13) The primary analysis plan for this study is to first evaluate the RCT and OBS studies separately using mixed model longitudinal regression analysis using an intent-to-treat approach. As was done in the SPORT analysis, assessment Intervals are treated as a fixed effect, meaning with each interval developed based on the date of intervention. Data gathered prior to date of intervention (DOI) will be considered baseline and fixed data points gathered after DOI will be classified according the form designation (e.g., 3mo, 6mo). Data points gathered after DOI that were not fixed points (e.g., complications, severe adverse events) will be associated with a fixed interval based on the length of time from the data point and DOI. A second random effects variable (Delta) will be created within each interval that reflects the distance (no. of days) between the actual observed point and the center of the fixed interval that this point falls within. Thus, patients may have multiple data points within a fixed interval and the distance orTime of data collection relative to DOI within each fixed interval will be included in the model. In addition, a Delta random variable, defined as the distance between the center of the fixed interval and the Time of data collect will, also be created. The primary analysis will regress the change in outcome (eg for the pcs outcome d_pcs) on baseline pcs (b_pcs), treatment, interval, site and patient age and sex,

For the RCT cohort, the base model for PCS would be

$$d_{\text{pcs}} = b_{\text{pcs}} \text{ treatment} | \text{interval} | \text{time site age sex}$$

A secondary analysis will replace time with the Delta variable with the model forcing the Delta covariate to have a value of 0 – thereby adjusting the results to reflect the expected value for the outcome as if the outcome was assessed at the exact center of the fixed interval.

$$d_{\text{pcs}} = b_{\text{pcs}} \text{ treatment} | \text{interval} \text{ delta site age sex} \text{ delta / delta} = 0$$

Where:

T_DOI = Date dependent variable was collected – DOI WITH negative T_DOI values indicating outcomes being assessed prior to treatment and positive T_DOI values indicating the time after DOI that the outcome was evaluated. Note that T_DOI values are nested within d_pcs
= -pcs-b_pcs (a positive change would reflect improvement)

b_pcs = baseline pcs

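### In the randomised cohort, baseline is anchored to the intervention rather than to assignment, so a long surgical wait can lead to re-baselining with the assignment known, almost only in the surgical arm

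*SAP*

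**What the plan says.** **Definition of baseline.** SAP Addendum 8/29/12 (modified 6/19/13): "Data gathered prior to date of intervention (DOI) will be considered baseline". The addendum does not mention randomisation here, and it does not say which record counts if several precede the intervention.

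**Baseline window.** Protocol 1.4 says that "patient reported HRQOL and treadmill tests must be completed within 6 months prior to intervention". Protocol 1.5.2 repeats the 6-month limit and says that baseline "data must be completed prior to intervention initiation". The Schedule of Events places Visit 0 from 6 months to 1 day before the intervention, with the intervention as Day 0.

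**Start of treatment.** Protocol 1.4, on the non-operative arm: "Nonoperative interventions will then be implemented as soon as possible". On surgery: "available dates for elective operative procedures may range from 1 to 6 months", and "operative intervention will take place within six months of treatment assignment".

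**Release of the assignment.** Protocol 1.5.2: "Randomization software will generate an intervention assignment upon completion of registration". Registration covers demographics and the inclusion criteria.

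**Use of baseline.** Under SAP 1.6 the outcome is change from baseline, with the baseline score as the main covariate. The primary outcome is the patient-reported SRS-QOL subscore (Protocol 1.5.1). The randomised cohort is analysed by intent to treat (SAP 1.6.1, Stage 3).

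**The concern.** In a randomised comparison the baseline score should be fixed before the patient knows her arm. Here the analysed baseline may be any score up to the intervention, and the time between assignment and intervention differs by arm: close to zero for non-operative care, 1 to 6 months for surgery. The outcome is self-reported and patients are not blinded. A score given while waiting for a known operation may differ from one given before assignment, whether from expectation or from a real change during the wait.

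If such a score replaces the pre-assignment one in the surgical arm only, the difference enters the change score and its covariate together. Randomisation then no longer protects that part of the comparison, although the protocol overview relies on the intent-to-treat analysis for its most valid estimate of the surgical effect.

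**Working it through.** **1. The plan's own figures.** SAP Table 2 assumes 80% power and two-sided alpha 0.05. A two-sample t-test reproduces all six sample sizes exactly: 24, 37, 64, 32, 50 and 87 per group. The two scenarios behind the SAP's 32-37 per group are:
- means 0.4 and 0.8, SD 0.6, n = 37: difference 0.4
- means 0.3 and 0.8, SD 0.7, n = 32: difference 0.5

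The documents give no figure for baseline timing or its effect.

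**2. When the window is missed.** Let g be the months from baseline to assignment and w the months from assignment to intervention. The baseline is outside the window when g + w > 6.
- Surgical example: g = 0.5, w = 5.75. The sum is 6.25, so the baseline is too old although surgery met its own 6-month limit.
- Surgery at w = 6: any g > 0 misses the window.
- Non-operative, w near 0: missed only if g > 6.

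**3. Share of the surgical arm affected (f).** Assume that waits are spread evenly over 1 to 6 months (the documents give no distribution) and that every missed window leads to a repeat. For g up to 5 months, f = [6 − (6 − g)]/5 = g/5.
- g = 0.5: f = 0.10
- g = 2.5: f = 0.50

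**4. Effect on the estimate.** Let d be the fall in score at a repeat and r the slope of follow-up score on baseline. If the shift does not carry into follow-up scores, the bias in the baseline-adjusted effect is about f × r × d, in favour of surgery for a fall and against it for a rise. Unadjusted change would be biased by f × d. A simulation with f = 1, r = 0.5, d = 0.2 gave 0.100 adjusted and 0.201 unadjusted, against 0.100 and 0.200 by formula. Baseline adjustment therefore shrinks the shift but does not remove it.

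Assumed r = 0.5 to 0.7 and d = 0.1 to 0.3:

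| f | Lowest | Highest | Share of planned difference |
|---|---|---|---|
| 0.1 | 0.1 × 0.5 × 0.1 = 0.005 | 0.1 × 0.7 × 0.3 = 0.021 | 0.005/0.5 = 1% to 0.021/0.4 = 5% |
| 0.5 | 0.5 × 0.5 × 0.1 = 0.025 | 0.5 × 0.7 × 0.3 = 0.105 | 0.025/0.5 = 5% to 0.105/0.4 = 26% |

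A bias of 0.025 gives a type I error of 0.054 (SD 0.6, n = 37) or 0.052 (SD 0.7, n = 32). A bias of 0.105 gives 0.117 or 0.092. At f = 0.1 the largest bias is 0.021, so the inflation is below the first pair.

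**5. Timing of the 24-month visit.** The two-year window is 24 to 28 months after intervention (Protocol 1.5.2). Counted from randomisation, it is about 24 to 28 months with w near 0. With w = 6 it is 24 + 6 = 30 to 28 + 6 = 34 months. The part due to arm is the wait itself, at most 6 months.

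**The case against.** Four points on the other side have force.

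- **First baselines are mostly early.** HRQOL scores help to identify candidates (Protocol 1.2) and are entry criteria (1.1). Questionnaires are given at study entry to all patients, and baseline data are to be entered within 24 hours of enrolment (1.5.2). A reader might infer that surgical patients routinely give their first baseline after learning their arm. The documents do not support that. These rules do not state whether the questionnaire precedes the assignment, and they are not carried into the SAP definition, but they largely close this route.
- **The repeat is inferred.** No section orders a second HRQOL, and the Schedule of Events has none between Visit 0 and month 3. A site could record a protocol variance instead. This stands: the window makes a repeat a natural response, not a stated requirement. It also stands that nothing bars one, and that the SAP would accept it as baseline.
- **A large f fits poorly with early baselines.** Under even waits, f = 0.5 needs baselines about 2.5 months before assignment. About 0.1 fits a half-month gap. This stands, and f = 0.5 is the high end.
- **Dating visits from the intervention is deliberate.** It is used consistently across the protocol and SAP. That is so, which is why the later surgical visit calls for a sensitivity analysis and not a change of schedule.

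**Conclusion.** The gap is real and confined to the randomised cohort; in the observational cohort patients choose their treatment, so the argument from randomisation does not apply. The SAP rule allows a post-assignment, self-reported score to serve as baseline, and the timing rules make that possible almost only in the surgical arm.

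The result can be biased by about 0.005 to 0.021 SRS points at f = 0.1 and 0.025 to 0.105 at f = 0.5, roughly 1% to 26% of the planned difference. This rests on assumed values of f, r and d, none of which the documents give, and on the shift not persisting into follow-up. With no repeats or no shift, the bias is zero.

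A reader might conclude that the plan does bias the trial towards surgery, or that a non-operative patient can never be affected. Neither is supported. The number of repeats and the sign of any shift are unknown, and a non-operative patient whose baseline is more than 6 months before the start of care would meet the same problem.

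**What to change.** **SAP Addendum 8/29/12, randomised cohort only:**
1. Replace the baseline rule with: the last SRS-QOL, ODI or SF-12 completed before the treatment assignment was generated. The date of randomisation alone is not enough, because it admits a form completed later the same day.
2. Keep any later pre-operative repeat as a separate record, never as baseline.
3. Where the only score is post-assignment, keep the patient in the intent-to-treat analysis with that score, flag it, report the number by arm, and give a sensitivity analysis.
4. Add a sensitivity analysis of the 24-month contrast by time since randomisation.

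**Protocol:** reconcile the intervention-based window in 1.4, 1.5.2 and the Schedule of Events with the 24-hour entry rule in 1.5.2.

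A data-entry gate that holds back the assignment until baseline is complete helps only while randomisation is open. The SAP's Addendum 1/17/13 says that it closed in July 2014, so the analysis rules are the part that can still act.

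**Cost:** a few sentences and some programming, provided that form completion and assignment times are held. The planned 32-37 per group is unchanged. The small downside is that some analysed baselines will be more than 6 months before surgery.
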